# **Chapter Three Patients, Materials and Methods**

A prospective comparative study was conducted in the High Institute for Infertility Diagnosis and Assisted Reproductive Technologies, Al-Nahrain University in Baghdad, from January 2023 to January 2024. Ninety Iraqi women were included in this study. Every patient gave her written informed consent before taking part in the study figure (3-1), which was approved by the Ethical Committee of High Institute for Infertility Diagnosis and Assisted reproductive Technologies, Al-Nahrain University. They were evaluated twice during the study period and they did not receive any monetary compensation for their participation.

# 3.1. Patients

A study involved a total of ninety women who were selected from those attended the High Institute for Infertility Diagnosis and Assisted Reproductive Technologies.

# 3.1.1. Patient classification

- Group A: patients who receive (700IU) of intrauterine hCG
- Group B: patients who receive (500IU) of intrauterine hCG
- Group C: Control group patients did not receive any treatment.

# 3.1.2. Inclusion criteria

• All couples undergoing IVF / ICSI protocols reaching the day of embryo transfer with grade 1 (G1) embryos.

• Age of women was (18-40) years old.

• Infertility due to female factors: tubal blockage, un ovulatory cycles, unexplained infertility.

- Infertility due to male factors.
- fresh cycle transfer

# **3.1.3.** Exclusion criteria

• All cases of endometrioses whether suspected clinically or diagnosed laparoscopically.

- Cases of congenital anomalies of the reproductive system.
- Patients aged more than 40 year
- Those not having G1 embryos.

• Cases with chronic systemic diseases (diabetes, blood disease, hypertension, connective tissue and autoimmune diseases, asthma, class II and III obesity, thyroid disturbance).

# 3.2 Materials equipment and tools

## 3.2.1. Equipment

The current study utilizes the tools, instruments, chemical substances and kits, outlined in Tables (3-1), (3-2) and (3-3).

Apparatus & Equipment	Company	Country
Air Incubator	Memmert	Germany
Automatic Pipette	Slammed	Germany
Centrifuge	Eppendorf	Germany
CO2 Incubator	Galaxy47/Eppendorf/	Germany
Collecting Tubes 1.5 ml	AFCO	Jordan

#### Table (3-1) Apparatus and Equipment

Dry Incubator	Fisher scientific	USA
EZ- tip RI	Cooper surgical fertility companies, Malov	Denmark
EZ-grip RI	Cooper surgical fertility companies, Malov	/Denmark
Flexible catheter (embryo transfer catheter	Gynetics	Ireland
Freezer	Concord	lebanon
Gel &Clot Activator Tubes	AFCO	Jordon
Glass Pasteur Pipette(150mm)	Poulten & Graf LTD	England
ICSI manipulator	Eppendorf/Nikon Te2000- 4	Germany
IUI catheter	Gyntics	Beligum
Laminar Flow Cabinet	K-Systems	Denmark
Light microscope	MEIJI	Japan
Medical suction machine	ARDO	Switzerland
Micropipette of 5-50, 100-1000µl	Thermo Scientific Nunc IVF Product	Denmark
Microplate reader capable of measuring absorbance at 450 nm	Human reader	Germany
Mini vidas Automated Immunoassay	BIOMRIEUX /	Italy
Ovum aspiration needle	Cook®	Australia
Pasteur pipette and tubes	Eppendorf	Germany
Pipette Tips (Yellow, Blue)	Brand	USA

Pipette Tips (Yellow)	Brand	Germany
Plain Tubes	AFCO	Jordon
Plastic rack	AFCO	Jordon
RI holding pipette	Cooper surgical fertility companies, Malov	/ Denmark
RI Spiked Injection Pipette	Cooper surgical fertility companies,Malov	Denmark
Semi-automaticmicroprocessorcontrolled photometer	Humalyzer Primus	/Germany
Scale (weight &height measure)	Health scale	China
Slides and cover slips		Germany
Stereomicroscope	Olympus/SZx16	Japan
Syringes (5ml, BD Discardit TM II)	Becton Dickinson	USA
Test tubes, Falcon petridish, Small dish,	Thermo Scientific Nunc IVF	Denmark
Center well dish, Four well dish, ICSI	Product	
dish		
Vaginal Sonography	Vesana Balance	china
Wash bottle	Brand	India

**3.2.2. Chemicals and drugs** The chemicals and drugs that used in this study are summarized in Tables (3.3 -3.4).

### Table 3.2: Chemicals and their manufactures

Chemicals	Manufacturing company/Country
Ferticult TM Aspiration	FertiPro NV/Belgium
FerticultTM Flushing medium	FertiPro NV/Belgium
FerticultTM Mineral oil	FertiPro NV/Belgium
Gain medium/ Early	FertiPro NV/Belgium
Hyaluronidase medium 80IU/ml	FertiPro NV/Belgium
PVP 10% in Flushing medium	FertiPro NV/Belgium

 Table (3-3): Drugs used in ICSI and their manufactures : Antagonist protocol

Trade Name	Chemical name	Company & country
Gonal f	Recombinant FSH 75u injection	Merk, Switzerland
Cetrotide®	Cetrorelix acetate for injection 0.25 mg	Merk, Switzerland
Oviltrelle	250 microgram hCG	Merk, Switzerland
Cyclogest	Natural Progesterone	CoxPharmaceuticals , Barnstaple, UK
hCG	Urinary human chorionic gonadotropin	Diclaire
Triptorelin	(Decapeptyl®) 0.1 mg vial	Ferring/ Germany

Chemicals and Kits	Company	Country
Human TNF Kit and IL_10 ELISA Kit	R&D Systems biotechne`brand	USA
Liaison FSH kit	Liaison	Italy
Liaison LH kit	Liaison	Italy
Liaison TSH kit	Liaison	Italy
Liaison PRL kit	Liaison	Italy
TOSOH E2 Kit	TOSOH AIA 600II	Japan

## 3.3. Methods

# 3.3.1. Patients' assessment and study design

A comprehensive medical, surgical, and obstetrical history was gathered from couples experiencing infertility, as per a structured questionnaire illustrated in figure (3-2). Thorough examinations were conducted on infertile women, encompassing both general and gynecological assessments. Height and weight measurements were taken to calculate the body mass index (BMI) using the formula BMI = weight (kg) / [height (m)]2. Initial hormonal evaluations were performed on either the second or third day of the menstrual cycle for all female subjects. Procedures such as transvaginal ultrasound, saline infusion sonography (SIS), and hysterosalpingography (HSG) were carried out to evaluate the uterine cavity, confirm tubal patency, and in some cases, laparoscopy was employed to assess tubal patency and exclude pelvic abnormalities. Seminal fluid analysis was conducted for the male partners. All infertile women enrolled underwent the application of the Gonadotropin Releasing Hormone (GnRH) antagonist ovarian hyperstimulation protocol, known as the flexible protocol. The follow-up of

patients included serial vaginal ultrasound and monitoring of serum estradiol levels. Subsequently, ovum pick up (OPU) was carried out post ovulation triggering approximately 35-36 hours later. Doppler ultrasound, along with measuring serum TNF and IL-10 levels, was performed for all participants on the day of OPU, followed by additional measurements on the day of embryo transfer. Evaluation of oocytes' morphology and recording of maturation rate (MR) were conducted, leading to Intracytoplasmic Sperm Injection (ICSI) of apparently normal Metaphase II (MII) oocytes. The morphological assessment of embryos was done, and the count of different embryo grades was noted. Luteal phase support, embryo transfer, and serum beta-human chorionic gonadotropin (B-hCG) evaluation were done on day 14 post embryo transfer, with the recording of biochemical pregnancy rate (Figure 3.3).

0.	Case no.		LMP		Protocol flexible antagonist day of cetrotide     type of trigger cd dose					
	age	HT.	WT.	BMI	Urasound	Base line US	5	Day of pick up	dıy Embrya	tranfer
and	Age	Occupant.	telephone		E.T. hype echoic (triple)					
					Hyper ochoic (non-triple)					
of infert.	duration				Sub endometrial flow RI					
					п					
of infer.	Tubal	Ovulatory	Male factor	Un e	VMAX					
eminal fluid analysis:		he			V MIN					
					1210	-				
Prog.A.\ Slow	R\	Non prog. C.	n. immo	tile Di	Number of corrects	W	10	GV	ahu	mul
		real prog. c.	many	and Dr.	, summer of oocyne	Day 1	2	3	4	s
• horm.assay C.D2-3		Type of gnt			No. of embryo & grade		-			
SH	cd2		9							
н	3		10		Embryo, Transfer	80 ,	da	N'	grade	
SH	4		11					r		
rolactine	5		12		Birchemical mer	Ler in Nord	day of pi	d q	day of th	aştır
esto.	6		13		184					
2	7		14		Interdation	r.18				
MH	8		15							
• Protocol flexible anta	gonist	day of cet	rotide		Pregn. test					

figure (3-2): Questionnaire

Figure(3-3): study design

# 3.3.2. Anthropometric measurement

The anthropometric parameters examined in the research primarily encompassed Body Mass Index (BMI), as determined by the subsequent criteria.

The computation of BMI involves dividing the weight in kilograms by the square of the height in meters (kg/m2). Subsequently, in accordance with WHO standards, females are categorized based on their BMI as follows:

those with a BMI  $\leq 18.5$  are classified as underweight,

individuals with a BMI of 18.5-24.9 are considered to have a normal weight,

those falling within the 25-29.9 range are classified as overweight, and

those with a BMI  $\ge$  30 are categorized as obese. The formula for calculating BMI is expressed as BMI = Weight in Kg ÷ (height in m)2.

# 3.3.3. Basal fertility workup

- Clinical and gynecological examinations were conducted along with basal ultrasound scanning via transvaginal route in order to rule out any potential abnormalities.
- Baseline hormonal evaluation was carried out during the early follicular phase (day 2 or 3 of the menstrual cycle) encompassing Follicle-Stimulating Hormone (FSH), luteinizing hormone (LH), and estradiol (E2). The assessment of hormones was executed employing an enzyme-linked fluorescent assay (ELFA) method, utilizing Minivids analysis apparatus (BIOMRIEUX/France).
- Viral studies were conducted for both partners.

# 3.3.4. Intracytoplasmic sperm injection program

## **3.3.4.1.a.** The flexible antagonist Protocol

A flexible antagonist protocol type was implemented for ICSI across all participants, with ovarian stimulation commencing once all parameters were within normal ranges. These parameters included an endometrium thickness of less than 5 mm, absence of any follicle exceeding 10 mm in the ovaries, and E2 levels below 50 pg/ml. The protocol entailed ovarian stimulation through daily subcutaneous injections of rFSH (Gonal F, Merk Serono)®, each containing 75IU per ampoule. The initial gonadotropin dosage was tailored based on individual factors such as age, antral follicle count, BMI, and previous responses to ovulation induction. Administration began on the second day of the menstrual cycle. Additionally, some participants were administered HMG vials (Menogon, Ferring Pharmaceutical) intramuscularly, each containing 75 IU of FSH and LH per vial, in accordance with their clinical needs. To address patient-specific requirements, a flexible regimen of GnRH antagonist (Cetrorelix acetate 0.25 mg, s/c Cetrotide®, Merck, Switzerland) was initiated once the primary follicle reached 13-14 mm. Serum E2 levels were throughout also monitored the procedure. 3.3.4.1.b.Triggering of ovulation

Induction of final oocyte maturation occurred when a minimum of three dominant follicles reached a size equal to or greater than 17–18 mm in diameter through the administration of subcutaneous recombinant hCG (Ovitrelle®, 6500 IU Merk serono, Switzerland), or initiation was facilitated by the use of a "dual trigger" comprising human chorionic gonadotropin (hCG) in combination with gonadotropin releasing hormone agonist (GnRH-a), specifically triptorelin (Decapeptyl; Ferring Pharmaceuticals) administered subcutaneously (. Le MT, et al. 2019)

## 3.3.4.2. Transvaginal ultrasound guided oocyte retrieval

A specialist recovered the oocytes 34–36 hours post-triggering, just prior to follicular rupture. Patients were admitted to the operating theatre in a fasting state, positioned lithotomy with an empty bladder, administered general anesthesia, and subjected to vaginal lavage with normal saline. Oocytes were retrieved from individuals under transvaginal ultrasound guidance using a delicate single lumen aspiration needle (Gynetics®, Belgium) connected to a Wallace oocyte recovery system. The opposite end of the needle was linked to a suction apparatus operating at 120-130 mm Hg. (Atzmon et al., 2020). Every follicle in both ovaries was aspirated and promptly transferred to the embryologist for meticulous examination to ascertain the constitution of the collected cumulus-oocyte complexes. Subsequent to completion, the needle was withdrawn, ensuring successful hemostasis. The entire procedure typically lasted between 20-30 minutes. Subsequently, patients received analgesics, antibiotics, and luteal phase support in the form of progesterone (Zheng et al., 2019).

#### **3.3.4.3.** Oocyte grading

The categorization of oocytes in terms of their maturity grade was conducted subsequent to the removal of the corona layers and cumulus. Subsequently, the oocytes underwent a thorough washing process and were examined under an inverted microscope to assess their stage of maturity and overall integrity. The evaluation of oocyte nuclear maturity relied on the presence of an extruded first polar body (PBI) within the perivitelline space and the absence of a germinal vesicle (GV). The germinal vesicle (GV) denotes the least mature oocyte where this circular structure is situated within the oocyte (refer to Figure 3.4, A). The MI stage represents an immature oocyte characterized by the absence of a polar body or germinal vesicle, serving as an intermediary phase between GV and MII

**Figure 3.4** depicts oocytes exhibiting varying degrees of maturity; (A) illustrates an oocyte classified as Germinal vesicle grade of maturity; (B) showcases an oocyte at Metaphase I grade of maturity; and (C) displays a typically mature metaphase II oocyte. This information was sourced from the esteemed High Institute for Infertility Diagnosis and Assisted Reproductive Technologies at AlNahrain University in Baghdad, Iraq.

According to Ozgur et al. (2015), the maturity index, or the proportion of mature oocytes for each participant, was determined using the following formula: Maturity index = (Total number of mature oocytes (MII) / Total number of oocytes retrieved)  $\times$  100.

## 3.3.4.4. Fertilization and Embryo Culture

## 3.3.4.4.a. Sperms Preparation

Usually before OPU, semen sample was prepared for sperm extraction. The sample was collected in a private room near the laboratory in order to limit the exposure of the semen to fluctuations in temperature and to control the time between collection and analysis. The sample was collected after a minimum of 2 days and a maximum of 7 days of sexual abstinence. The sample was obtained by

masturbation and ejaculated into a clean, wide-mouthed container made of glass or plastic, from a batch that had been confirmed to be non-toxic for spermatozoa. The specimen container was kept at ambient temperature between 20 °C and 37 °C to avoid large changes in temperature that may affect the spermatozoa after they were ejaculated into it. It was labeled with the man's name, identification number, date and time of collection. The specimen container was placed in the incubator (37 °C) while the semen liquefied. In men with azoospermia Testicular Sperm Extraction (TESE) is a surgical sperm retrieval procedure used as infertility treatment. It was done by removing a small portion of tissue from the testicle under general anesthesia and extracting the few viable sperm cells presented in that tissue for ICSI.

## 3.3.4.4. b. Intracytoplasmic sperm injection procedure

At the IVF lab, aspirated follicles were immediately examined in a petri dish. The oocyte was retained in the CO2 incubator at 37°C for one to two hours after flushing. Following that, each oocyte was graded and stripped in the laminar flow cabinet.

The mature oocyte was grasped using a specialized holding pipette, and one chosen sperm with normal morphology was immobilized and picked up using an ICSI microscope and a very thin, pointed, hollow needle. The oocyte's shell was then gradually punctured with the needle. (with PB at 12 or 6 o'clock) into its cytoplasm (Figure 3.5). To reduce the possibility of chromosomal or spindle damage, the genetic material is kept away from the injection site because it is anticipated to be adjacent to the PBI. Once the sperm were carefully injected into the cytoplasm and the needle was taken out, the sample was kept in a CO2 incubator to await the potential result of fertilization.

**Figure 3.5**: ICSI Micromanipulation, Polar body at 12 or 6 o'clock in ICSI images, adapted from Al Nahrain University, Baghdad, Iraq's High Institute for Infertility diagnosis and Assisted Reproductive Technologies

## **3.3.4.5.** Evaluation of fertilization and embryo grading :

Figure 3.6 illustrates the assessment of injected oocytes, which was carried out 16–18 hours after the ICSI to approve fertilization (Zygotes) and ensure the presence of two polar bodies and two pronuclei. If the fertilized oocytes had either 1PN or 3PN, they were deemed abnormal. It was considered that oocytes lacking PN were not fertilized. The following formula was utilized to calculate the fertilization rate: The calculation of fertilization rate is (total number of injected MII retrieved oocytes / number of fertilized oocytes (2PN) times 100 (Magaton et al., 2023).

Figure 3.6. Fertilized oocyte (appearance of two pronuclei) is an indicator of fertilization (Merchant et al. 2011)

First-day cleavage was assessed 24 hours after fertilization, and the number and size of blastomeres in each embryo were counted. On days 2 and 3 (48 and 72 hours after oocyte harvest), the amount, size, symmetry, and percentage of blastomere fragmentation determine how the embryos are graded. As seen in Figures 3.7–3.9, the developing embryos were morphologically graded according to the Istanbul consensus workshop prior to embryo transfer, where the embryo was classified into grades I, II, and III (Balaban et al., 2011).

Figure (3-7): Stages of human pre-implantation embryo development. Phase-contrast images of human embryo development from day (d) 0 to day 3. Following fertilization, embryos undergo a series of mitotic cell divisions. A: Zygote, B: 4 cells Grade 1, C: 8cells Grade 1(High Institute for Infertility Diagnosis and Assisted Reproductive Technologies, Al-Nahrain University, Iraq, Baghdad, 2023).

Grade II: High quality, most cells have stage-specific cell sizes, even in cell division embryos with 10–25% fragmentation.

Figure 3.8: Adapted from the High Institute for Infertility diagnosis and Assisted Reproductive Technologies, Al Nahrain University, Baghdad, Iraq; Day 3 grade 2 embryo 8 cells, equal size, 20% fragmentation

Grade III: Embryos of fair quality that show signs of multinucleation, fragmentation (>25%), and uneven cell division.

**Figure 3.9:** Adapted from the High Institute for Infertility diagnosis and Assisted Reproductive Technologies, Al Nahrain University, Baghdad, Iraq, Day 3 grade 3 embryos (5–6) cells, uneven, >25% fragmentation.

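### The fertilization-rate formula in Protocol 3.3.4.5 is inverted: no defined value can be below 100%, and a higher value means worse fertilization

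*Protocol*

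**What the plan says.** Protocol section 3.3.4.5 introduces the formula as the one applied in the study: "The following formula was utilized to calculate the fertilization rate". It then gives the ratio as "total number of injected MII retrieved oocytes / number of fertilized oocytes (2PN) times 100".

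The same section fixes how the two counts relate. The pronuclear check 16–18 hours after ICSI "illustrates the assessment of injected oocytes, which was carried out" on those oocytes only. Of the results, "It was considered that oocytes lacking PN were not fertilized", and oocytes with one or three pronuclei are classed as abnormal. Section 3.3.1 says the oocytes chosen for injection were apparently normal MII oocytes.

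Section 3.3.4.3 defines the parallel laboratory measure as a part over a whole, for each participant: "Maturity index = (Total number of mature oocytes (MII) / Total number of oocytes retrieved", times 100.

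Fertilization rate is named only in section 3.3.4.5. Section 3.3.1 mentions "recording of maturation rate (MR) were conducted", says that "the count of different embryo grades was noted", and lists the biochemical pregnancy rate, but not a fertilization rate. The SAP's statistical analysis paragraph applies t-tests and ANOVA to continuous variables without naming them.

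**The concern.** A fertilization rate should be the percentage of injected oocytes that fertilize normally, between 0% and 100%, with higher values better. The printed ratio has the two counts in the opposite order. It cannot fall below 100%, its direction is reversed, and it has no value when no oocyte fertilizes.

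This is an operational definition in the methods chapter of a study whose title names ICSI outcome. A reader who follows it gets a number that is not a fertilization rate. If it was used, a group with a higher mean could be read as fertilizing better when it fertilized worse. Reversing the direction of the reported means afterwards would not reliably repair this, as the working shows.

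**Working it through.** The documents give no fertilization-rate value and no oocyte counts, so there is no figure to reproduce. The check is of the formula itself, and all counts below are illustrative.

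**Inputs**
- Printed formula: injected MII / 2PN × 100 (Protocol 3.3.4.5).
- Relation of the counts: 2PN ≤ injected MII, because the check is made on injected oocytes and those with no, one or three pronuclei are not counted as 2PN (Protocol 3.3.4.5).
- Comparator: the maturity index, MII / retrieved × 100 (Protocol 3.3.4.3).

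**Step 1: range.** Since 2PN ≤ injected, injected / 2PN ≥ 1, so the printed value is at least 100%. It equals 100% only when every injected oocyte shows 2PN, and it is undefined when 2PN = 0. Running all 820 pairs with 1 ≤ 2PN ≤ injected ≤ 40 gave no value below 100%.

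**Step 2: direction.** With the number injected held fixed, the printed value fell strictly as 2PN rose in every case. A higher value always means a smaller fertilized proportion.

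**Step 3: size for one woman.** Let p = 2PN / injected × 100. Then printed value = 10,000 / p. With 10 oocytes injected:

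| 2PN | True rate | Printed value |
|---|---|---|
| 10 | 100% | 100% |
| 8 | 80% | 125% |
| 7 | 70% | 142.9% |
| 5 | 50% | 200% |
| 2 | 20% | 500% |
| 1 | 10% | 1000% |

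The value depends on the proportion, not the count: 2 of 2 prints as 100%, and 6 of 20 prints as 20 / 6 × 100 = 333.3%.

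**Step 4: group means, assuming one ratio per woman.** Take two women with 8 of 10 and 2 of 10.
- True mean: (80 + 20) / 2 = 50%.
- Printed mean: (125 + 500) / 2 = 312.5%.
- Inverting the printed mean: 10,000 / 312.5 = 32%, not 50%.

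In general, inverting the printed mean gives the harmonic mean of the women's rates. That is never above the ordinary mean and equals it only if all the rates are equal. The printed mean is pulled towards women with a low fertilized proportion.

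**Step 5: ranking of groups.** Group X: 9, 9 and 1 of 10. Group Y: 5, 5 and 5 of 10.
- True means: X = (90 + 90 + 10) / 3 = 63.3%; Y = 50%.
- Printed means: X = (111.1 + 111.1 + 1000) / 3 = 407.4%; Y = 200%.

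A reader who knew the scale was reversed would take X as the worse group, although its true mean is higher. Reversing the direction of reported means is therefore not a safe correction.

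**The case against.** The strongest reply is that this is a drafting slip with nothing resting on it. The sentence repeats its own lead-in and has an unclosed parenthesis, and the maturity index is written correctly, so the authors evidently know the part-over-whole form. Fertilization rate is not among the items section 3.3.1 lists as recorded, the SAP names no comparison of it, and the study period (January 2023 to January 2024) is over. The hCG was infused after ovum pick-up (sections 3.3.9 and 3.3.9.1). Fertilization took place in the laboratory, where after injection "the sample was kept in a CO2 incubator to await the potential result of fertilization" (section 3.3.4.4.b). The rate therefore describes the cycle and is not a plausible effect of the intervention.

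Much of this stands. A slip in writing is at least as likely as a miscalculation, and the pregnancy, Doppler and cytokine comparisons rest on serum β-hCG, flow velocities and serum assays (sections 3.3.8, 3.3.7.2 and 3.3.5.1). It limits the consequences but does not make the formula right: the text states that this formula was used, and nothing else in either document corrects it.

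A second point is that section 3.3.4.5 does not say the ratio was taken per woman. If counts were pooled by group, 10,000 divided by the printed value returns the pooled rate exactly, and steps 4 and 5 fall away. That is correct. The per-woman reading is the more natural one, given the wording for the maturity index and the SAP's presentation of data as means and standard deviations, but it remains an assumption. Steps 1 to 3 do not need it.

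The fraction is written inline with a slash, so the order of its terms is unlikely to be an artefact of reading the PDF.

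**Conclusion.** The concern holds. As printed, the formula gives the reciprocal of the fertilization rate: at least 100% whenever it is defined, rising as fertilization worsens, and equal to 10,000 divided by the true percentage. This follows from the section's own description of the counts and needs no outside assumption.

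Whether any data were calculated this way is unknown, and without counts the size of any effect in this study cannot be stated. The statement that group means cannot be converted back assumes one ratio per woman. The error is worth correcting because it sits in an operational definition, but its reach is limited: no comparison named in the documents depends on it.

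**What to change.** In Protocol section 3.3.4.5, replace the formula with: fertilization rate = (number of 2PN oocytes / number of MII oocytes injected) × 100. State whether it is calculated for each woman, as the maturity index is.

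Then state whether a fertilization rate was calculated at all. If not, the text correction is enough. If it was, recompute it for each woman from the laboratory counts and compare it with the stored value. A stored value above 100% is a warning sign but not proof, since a miscount could also produce it. If the inverted ratio was used, rerun any summary or comparison that relied on it from the counts; do not invert group means.

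The cost is one line of text and, if a rate exists, a short data check. The check needs the injected and 2PN counts from the laboratory records. The legible part of the questionnaire (figure 3-2) has related entries, such as number of oocytes and embryo number and grade, but no explicit field for either count. Its text is too garbled to show that the counts were not collected.
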